#### **Statistical Analysis Plan:**

**Design:** This is an exploratory single center, open-label design study in approximately 12 patients. Safety of Taltz (Ixekizumab) in the treatment of the autoimmune blistering disease, BP will be evaluated. Changes in new blister formation will also be explored.

**Primary Endpoint:** The primary endpoint will be median time from first dose of Taltz (Ixekizumab) treatment to cessation of any new blisters.

**Secondary Endpoint(s):** The secondary endpoints will include change in BPDAI from day 0 to week 12, total dose of prednisone required during the therapeutic time period at weeks 0-12. Additional analysis will be performed on serological markers, disease activity after drug discontinuation, and safety monitoring. Descriptive statistics and graphical plots will be mainly used to summarize the data and estimate primary and secondary endpoints.

**Primary Analysis:** Calculation of the time from first dose of treatment until cessation of any new blisters will be conducted and summarized using means, standard deviations and 95% confidence intervals. Blister formation will be summarized at baseline and subsequent time points (using means, standard deviations and 95% confidence intervals). Change in blister formation (any new blisters) from baseline will be calculated by subtracting the baseline number of blisters from the number of blisters at each evaluation. Graphical displays will be produced; such as mean profile plots or bar charts.

**Secondary Analyses:** Analyses for secondary endpoints will also be descriptive in nature. Adjustment for multiple comparisons for the secondary analyses will not be done due to the exploratory nature of this research. Calculation of the change in BPDAI score from baseline to week 12 will be conducted and summarized using means, standard deviations and 95% confidence intervals. Graphical displays will be produced; such as mean profile plots or bar charts.

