#### **Primary Endpoint:**

Median time from first dose of Taltz (ixekizumab) treatment to cessation of new blisters.

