#### **Primary Outcome Measures:**

Median time from first dose of Taltz (Ixekizumab) treatment to cessation of new blisters. The study subject will undergo physical examination and assessment for cessation of new blister formation via physical examination and standard full body photography.

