
#### **Sample Size Computation and Power Analysis:**

The sample size for this pilot study is set at 12 patients for logistical and financial reasons. This is similar in size to other exploratory studies and will provide adequate data for estimation purposes for planning future studies. With 12 patients, the study is intended to be for estimation purposes only.

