## **Supplementals:**

### **Supplemental 1: Appropriateness of Measures**

According to expert consensus guidelines on BP, new blister formation is a defining feature of disease activity. (6) Disease control is defined as the cessation of new blister formation. The consolidation phase is defined as the phase with no new blister formation in 2 weeks and healing of lesions. Transient lesions heal within 1 week and non-transient lesions are does not heal within 1 week. Complete remission is defined by, no new blisters within 2 months, on or off therapy. Partial remission is defined by transient lesion formation. New, mild disease activity is defined by the formation of less than 3 lesions per month and a disease flare is defined by 3 or more lesions in a month. Therefore, we will be required to monitor for the time to cessation of new blisters as surrogate for disease control as well as the formation of new blisters throughout the study.

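### The primary endpoint is a median time to cessation of new blisters, but the only summary planned for that time is a mean, with no rule for patients who never stop blistering

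*Combined protocol and SAP*

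**What the plan says.** The endpoint is a median wherever it is defined. The Project Overview has "Median time from first dose of Taltz (ixekizumab) treatment to cessation of new blisters", Primary Outcome Measures has "Median time from first dose of Taltz (Ixekizumab) treatment to cessation of new blisters", and the Statistical Analysis Plan has "The primary endpoint will be median time from first dose of Taltz (Ixekizumab) treatment to cessation of any new blisters". The Objectives paragraph of the overview and the Primary Objectives section agree.

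The Primary Analysis paragraph of the same plan names one method for this time: its calculation "until cessation of any new blisters will be conducted and summarized using means, standard deviations and 95% confidence intervals". The rest of the paragraph concerns blister counts, not time: "Blister formation will be summarized at baseline and subsequent time points (using means, standard deviations and 95% confidence intervals"), then change from baseline and graphs.

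A general sentence under Secondary Endpoint(s) reads "Descriptive statistics and graphical plots will be mainly used to summarize the data and estimate primary and secondary endpoints". It does not exclude a median, but it names no estimator.

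No section mentions censoring, Kaplan-Meier estimation, a confidence interval for a median, or a value for a patient who never stops blistering, withdraws or is lost. No section states whether week 12 or week 18 closes the observation period for the primary endpoint.

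**The concern.** There are two faults, and they compound each other.

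1. **Wrong quantity.** Times to an event are usually skewed, so their mean and median differ. An analyst who follows the Primary Analysis paragraph reports something other than the endpoint.
2. **Undefined for some patients.** A patient still forming blisters at the last visit has no cessation time. A mean over all 12 patients then needs a rule: leave the patient out, or substitute a value. Each rule gives a different answer. Such patients are foreseeable, because the study enrols treatment-refractory disease and observes it for 18 weeks at most.

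The sample size section says the data "will provide adequate data for estimation purposes for planning future studies" and that the study is for estimation only. No hypothesis is tested, so the primary estimate is the study's main product. The study is also open-label, so a choice that sets the result should be fixed before the data are seen.

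**Working it through.** **Inputs from the documents.** There are 12 patients (sample size section). Treatment lasts 12 weeks and follow-up a further 6 (Research Design). Visits are at weeks 2, 4, 6, 8, 10, 12 and 18 (Table-2). The sample size was set for logistical and financial reasons, so there is no derived figure to reproduce.

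**Example that needs no distribution.** Suppose 8 patients stop blistering at weeks 2, 2, 4, 4, 6, 6, 8 and 10 (sum 42), and 4 never stop.

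| Handling of the 4 patients | Mean (weeks) | 95% CI (t) |
|---|---|---|
| Left out | 42/8 = 5.3 | 2.9 to 7.6 |
| Set to week 12 | (42 + 48)/12 = 7.5 | 5.0 to 10.0 |
| Set to week 18 | (42 + 72)/12 = 9.5 | 5.3 to 13.7 |

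The Kaplan-Meier curve falls to 6/12 at week 6. The median is therefore 6 weeks (7 by the midpoint convention), whichever window is used. The interval from the 3rd to the 10th ordered time has exact coverage 96.1% and runs from week 4 to not reached. The log-log interval runs from week 2, where S = 10/12 and its lower limit of 0.48 is already below 0.5, to not reached.

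**How often a rule is needed.** Assumptions, not in the documents: exponential times, no dropout, true medians of 6, 12 and 24 weeks. The chance that a patient stops within the window is p = 1 − 0.5^(window/median). The chance that at least one of 12 does not is 1 − p^12.

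| True median (weeks) | p, week 12 | At least one without cessation | p, week 18 | At least one without cessation |
|---|---|---|---|---|
| 6 | 0.75 | 97% | 0.875 | 80% |
| 12 | 0.50 | >99% | 0.65 | 99% |
| 24 | 0.29 | >99% | 0.41 | >99% |

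**What the planned mean would report.** I simulated 100,000 trials per scenario, with each time recorded at the next scheduled visit. Coverage is the share of t-based 95% intervals that contain the true median; where patients are left out, it is taken among trials with at least 2 cessations.

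| Window and handling | Mean (weeks) at true median 6 / 12 / 24 | Coverage |
|---|---|---|
| Week 12, left out | 5.7 / 6.3 / 6.7 | 92% / 18% / 11% |
| Week 12, set to 12 | 7.3 / 9.2 / 10.4 | 84% / 29% / 0% |
| Week 18, left out | 7.5 / 9.0 / 9.8 | 93% / 75% / 15% |
| Week 18, set to 18 | 8.8 / 12.2 / 14.7 | 77% / 94% / 0% |

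With the week-12 window and such patients left out, a fourfold change in the true median moves the reported mean by one week. Setting them to week 12 separates the drugs, but overstates a 6-week median and badly understates a 24-week one.

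**What the alternative can deliver.** With complete follow-up, the Kaplan-Meier median is reached if at least 6 of 12 patients stop. The chance that it is not reached is P(Binomial(12, p) ≤ 5): 1%, 39% and 89% with a week-12 window, and <1%, 9% and 65% with week 18.

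Its upper limit is finite only if the log-log upper limit of S falls below 0.5. The standard error of log(−log S) is √[(1 − S)/(12S)]/|ln S|:

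- 9 events: S = 0.25, standard error 0.361, upper limit 0.25^(1/e^(1.96 × 0.361)) = 0.505.
- 10 events: S = 0.167, standard error 0.360, upper limit 0.413.

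So 10 events are needed. With a week-12 window the upper limit is open with probability P(Binomial(12, p) ≤ 9): 61%, 98% and >99%.

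**The case against.** - **The general sentence on descriptive statistics leaves room for a median.** It does, but it sets no estimator, no interval and no rule for patients without cessation. The specific sentence in the Primary Analysis paragraph prescribes means.
- **The Primary Analysis is more than this mean.** Blister counts by visit, and the change in BPDAI among the secondary analyses, would show treatment failure. They do not estimate a time, so they do not repair the primary estimate.
- **Week 12 is the natural window.** This has weight. Research Design expects a response by week 12, and the secondary outcomes treat weeks 12 to 18 as activity after stopping the drug. The Supplemental 1 phrase "as well as the formation of new blisters throughout the study" concerns later blister formation rather than the cessation time, so it is weak evidence for week 18. But week 12 is nowhere stated. If it is accepted, the spread at a true median of 12 weeks narrows to 6.3 versus 9.2 weeks.
- **The size rests on assumptions.** This is true of the simulation. The 24-week case lies beyond an 18-week study, so its near-zero coverage when patients are set to the last visit is largely built in. Some of the error is rounding up to visits: at a 6-week median about 0.8 week of the 7.3 comes from that. The worked example needs no distribution and shows the same dependence.
- **The study is exploratory, with no test or error rate at risk.** This is also true, but it leaves the estimate as the main result.

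**Conclusion.** The concern holds and should be corrected before analysis. The stated analysis of the primary time variable targets a different quantity from the endpoint, and it cannot be carried out on all patients without a choice the plan does not make. That choice moves the result substantially: 5.3, 7.5 or 9.5 weeks from the same 12 hypothetical patients, and 6.3 to 12.2 weeks on average at a true median of 12 weeks. The mismatch and the missing rule follow from the text alone. The averages, coverages and not-reached rates rest on assumed exponential times, no dropout and the scheduled visits. Rates at other true medians would differ, but with a week-12 window a rule would be needed in nearly every trial across the range examined.

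**What to change.** In the Primary Analysis paragraph:

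1. Replace the mean and SD summary of the time with the Kaplan-Meier median and its log-log 95% confidence interval. Censor patients without cessation at their last blister assessment, and report the median or its upper limit as not reached where that applies.
2. State whether week 12 or week 18 closes the window.
3. Add the proportion of all treated patients with cessation by week 12, with an exact (Clopper-Pearson) 95% interval, and the number who never stop.
4. State how the analysis treats early withdrawal, rescue prednisone and blistering that resumes. Censoring early withdrawals may be informative.

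Interval-censored (Turnbull) estimation is optional, given the two-weekly visits.

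The drawback is limited precision. With a week-12 window the median is often not reached for a weak drug, and its upper limit is usually open. The proportion is therefore needed beside it, and it is also imprecise: 9/12 gives 43% to 95%, 6/12 gives 21% to 79%, and 3/12 gives 5% to 57%.

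The cost is SAP wording only, with no new data, visits or patients.

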## **Publication Strategy:**

The key design elements of this protocol will be posted in a publicly accessible database such as [clinicaltrials.gov](http://clinicaltrials.gov). In addition, upon study completion and finalization of the study report the results of this trial will be either submitted for publication and/or posted in a publicly accessible database of clinical trial results.

**Tables:****Table-1: Prohibited treatment**

Prohibited treatments†,‡	Washout period (before Randomization Visit)
Taltz (Ixekizumab)	No prior use allowed
Any biologic drug directly targeting IL-17 or the IL-17 receptor (other than Taltz (Ixekizumab), e.g., brodalumab, secukinumab)	No prior use allowed
Other systemic immunomodulating treatments § [e.g., methotrexate, cyclosporine A, corticosteroids (oral, i.v., intramuscular, s.c., intra-articular, transdermal)  , mycophenolate mofetil, azathioprine ]	4 weeks
Topical treatment that is likely to impact signs and symptoms of BP (e.g., pimecrolimus, tacrolimus)	2 weeks
Live virus vaccinations	6 weeks
Non-immunosuppressive agents (tetracycline antibiotics & niacinamide)	2 weeks
Prohibited regimen of Topical Corticosteroids (TCS)	
TCS on any location on body (including face, scalp and/or genitoanal area)	2 weeks
Non-BP Therapy	Stable period (before Randomization Visit)
Any other treatment known to worsen BP (angiotensin converting enzyme inhibitors & furosemide)	Stable at least 4 weeks before randomization

-subjects may be on up to 20mg of oral prednisone but must be on a stable dose prior to initiation of ixekizumab

† If the prohibited treatment is being used during the study for any indication, the subject must discontinue use of the prohibited treatment if he/she wishes to continue in the study.

‡ In case of undue safety risk for the subject, the subject should discontinue study treatment at the discretion of the investigator/qualified site staff. If the subject received a live virus vaccination during the study, the subject must discontinue study treatment.

§Inhalative CS with only a topical effect (e.g., to treat asthma) are not considered “**systemic** immunomodulating treatments” and are therefore acceptable as co-medication.

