The current therapeutic hierarchy, based upon randomized controlled trials (RCTs), for BP is largely reliant upon oral (up to 0.75mg/kg of prednisolone or prednisone) and topical (up to 40g of clobetasol daily) corticosteroids as well as adjuvant steroid sparing agents (azathioprine or mycophenolate mofetil). (11-14) A slow taper of oral corticosteroids is considered first-line for disease requiring systemic therapy. Therefore, the use of prednisone as a rescue therapy will allow for the assessment of Taltz (Ixekezumab) as a steroid sparing agent. Non-RCT based immunosuppression with rituximab and methotrexate have also been reported to be successful. (15, 16) Non-immunosuppressive agents including doxycycline, tetracycline, and niacinamide are reported to improve disease; however, only tetracycline and niacinamide have been compared to immunosuppressive agents. (17) There is one ongoing trial comparing doxycycline to prednisone in BP. (18)

Recently, IL-17 has been identified as a key driver of chronic inflammation in BP. (5) IL-17 inhibition may provide a much needed and more targeted treatment, with a better side effect profile. Taltz (ixekizumab) is a recombinant high-affinity fully human monoclonal antibody that targets IL-17A IgG1/kappa-class. Taltz (ixekizumab) neutralizes IL-17A and targets the Th17 pathway, which has been clearly shown to be involved in the pathogenesis of psoriasis with unprecedented responses. (7) In addition, the safety profile of Taltz (ixekizumab) is similar to that of etanercept with rare infectious complications. The clinical effects of targeting Th17 cells through IL-17A neutralization remain an unknown but attractive therapy in BP. The timing of targeting is paramount as prior studies in psoriasis often involve individuals with chronic plaque psoriasis in which there may be a larger percentage of Th17 cells. Therefore, the effects of Taltz (ixekizumab) in BP may be dependent upon the duration of disease prior to the institution of therapy.

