### **Concomitant Medications:**

Concomitant medications are allowed if not listed in [Table-1](#). Oral corticosteroids will be allowed as a rescue medication. Stable doses of oral corticosteroids will be permitted at enrollment of the study, with a maximum dose not to exceed 20mg/day of prednisone or its equivalent. For patients on oral corticosteroids, Calcium 1200mg and Vitamin D 800 IU will be prescribed. For individuals with recurrent cellulitis or recurrent candidiasis, antimicrobials will be prescribed (see Exclusion Criteria). Dose adjustments of these medications should be avoided during the study. Drug-induced cases of BP will be excluded. Subjects who are receiving treatments known to worsen BP (angiotensin converting enzyme inhibitors & furosemide) must be on stable dose for at least 4 weeks prior to enrollment. Topical corticosteroids (TCS) are not allowed during the entirety of the study. Oral corticosteroids, as a rescue means (see [Supplemental 4](#)), will be allowed. After the screening period, the use of concomitant medication for BP in all body regions is restricted to bland emollients and other non-medicated interventions (not listed in [Table-1](#)) Use of bland emollients must be recorded. Preferred

emollients include Vaseline, Vanicream, and Vaniply. The definition of “bland” excludes all topical medications that contain pharmacologically active ingredients. Once the subject is screened and if the subject has intolerable blistering, scaling, and/or itching, the use of bland emollients is permitted. The use of bland emollients should be avoided during the 12 hours preceding a scheduled study visit.

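### The SAP has no rule for a blister cessation first seen after on-study use of a prohibited BP treatment, so as written it enters the time-to-cessation estimate for ixekizumab

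*Combined protocol and SAP*

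**What the plan says.** **Prohibited treatments.** Table-1 lists topical corticosteroids, topical calcineurin inhibitors, tetracyclines and niacinamide, and systemic agents such as methotrexate, cyclosporine, mycophenolate, azathioprine and corticosteroids. The Introduction presents most of these as BP therapies; for example, "Non-immunosuppressive agents including doxycycline, tetracycline, and niacinamide are reported to improve disease". Under Concomitant Medications, "Topical corticosteroids (TCS) are not allowed during the entirety of the study", and after screening "the use of concomitant medication for BP in all body regions is restricted to bland emollients and other non-medicated interventions".

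**Consequence of a breach.** Footnote † covers on-study use whatever the reason for it, and its one requirement is that "the subject must discontinue use of the prohibited treatment if he/she wishes to continue in the study". Footnote ‡ gives two grounds for stopping ixekizumab. One is discretionary: "In case of undue safety risk for the subject, the subject should discontinue study treatment at the discretion of the investigator/qualified site staff". The other does not concern a BP treatment: "If the subject received a live virus vaccination during the study, the subject must discontinue study treatment".

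**Permitted corticosteroid.** A stable baseline dose of up to 20 mg/day prednisone is allowed (Table-1, footnote 1; Concomitant Medications), and "Oral corticosteroids will be allowed as a rescue medication", under Supplemental 4.

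**Endpoint and analysis.** The primary endpoint is the median time from first dose to cessation of new blisters. The primary analysis reads "Calculation of the time from first dose of treatment until cessation of any new blisters will be conducted", summarised by means, standard deviations and 95% confidence intervals. The SAP gives no intercurrent-event rule, censoring rule, per-protocol set or sensitivity analysis for other BP treatment.

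**The concern.** The protocol foresees prohibited use and keeps the patient in the study, but never says what happens to that patient's outcome. Suppose an outside physician gives topical steroid or a tetracycline at Week 4 and the patient has no new blisters at Week 6. The endpoint as written gives a time of 6 weeks from first ixekizumab dose.

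There is no control arm against which to judge the contribution of the other treatment. Research Design says the study will assess ixekizumab as monotherapy, and Sample Size Computation says the estimates are for planning future studies, so an over-favourable time would carry forward. The objective measures that Research Design offers against bias deal with how outcomes are assessed, not with co-treatment. It is plausible, though the documents do not say so, that patients whose blistering persists are the most likely to be given something else. The Week 12 BPDAI change has the same gap.

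**Working it through.** **Step 1: is there a handling rule?** The places that could contain one are these.

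| Place | What it governs | Effect on the endpoint |
|---|---|---|
| Table-1, footnote † | Remaining in the study after prohibited use | None stated |
| Table-1, footnote ‡ | Stopping ixekizumab (safety risk, live vaccine) | None stated |
| Concomitant Medications | What is allowed or banned | None stated |
| Primary Outcome Measures | Endpoint and how it is assessed | No condition on other treatment |
| Statistical Analysis Plan | Summary statistics | No condition on other treatment |

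So a cessation after prohibited use is included by default.

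**Step 2: does the protocol treat recent use as relevant?** Yes. Before study drug it requires 2 weeks of washout for topicals, tetracyclines and niacinamide, and 4 weeks (or 5 half-lives, if longer, in Research Design) for systemic immunosuppressants. On treatment, visits are every 2 weeks and no equivalent interval is required after on-study use. An assessment can therefore fall inside a period that the protocol itself considers too soon at entry.

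**Step 3: is there a plan figure to reproduce?** No. The sample size of 12 was set for logistical and financial reasons, without alpha, power or a precision target. The figures below are illustrations on assumed inputs.

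**Step 4: chance of any affected patient.** Assume each of 12 patients independently has probability q of prohibited BP-active use. P(at least one) = 1 − (1 − q)^12, and P(at least two) = 1 − (1 − q)^12 − 12q(1 − q)^11.

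| q (assumed) | At least one | At least two |
|---|---|---|
| 5% | 46% | 12% |
| 10% | 72% | 34% |
| 20% | 93% | 73% |

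**Step 5: effect on the median.** Assume cessation at weeks 2, 2, 4, 4, 6, 6, 8 and 10, with four patients not ceased at Week 12. Take the median as the first time at which the Kaplan-Meier proportion not ceased is 0.5 or less. With all counted, S(6) = 6/12, so the median is 6 weeks. Now let one, two or three cessations (at weeks 4, 6 and 8, in that order) follow prohibited use and be carried as not ceased.

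| Cessations not counted | Ceased | Median | Mean of observed times |
|---|---|---|---|
| 0 | 8/12 | 6 weeks | 42/8 = 5.25 |
| 1 | 7/12 | 8 weeks (S = 6/12) | 38/7 = 5.43 |
| 2 | 6/12 | 10 weeks (S = 6/12) | 32/6 = 5.33 |
| 3 | 5/12 | not reached (S = 7/12) | 24/5 = 4.80 |

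Censoring these patients at the visit before cessation gives the same medians: 8 weeks, 10 weeks and not reached.

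**Step 6: can the planned summary carry the rule?** No. The mean in the last column omits everyone who has not ceased. It hardly moves, and it even falls when three cessations are removed. A mean and standard deviation cannot represent a patient who has not ceased.

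**The case against.** **Silence is not a rule.** A reader might infer that the plan declares such a cessation to be an ixekizumab response. It does not. Footnote † governs study participation, and the SAP never defines a response. What stands is narrower: the endpoint as written includes these cessations and nothing removes them.

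**Footnote † is not the defect.** A reader might infer that patients with prohibited use ought to leave the study. The documents give no support for that, and staying preserves follow-up and safety data. The gap is in the analysis.

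**Prednisone is the larger co-treatment.** The protocol openly permits baseline prednisone and offers rescue at baseline and at the 2-weekly visits, so it would be wrong to argue that attribution depends on no other active treatment at all. This stands. It narrows the attribution argument and shows that prednisone needs its own rule. It does not justify leaving unpermitted treatments unaddressed. Because Table-1 lists oral corticosteroids, a rule referring loosely to Table-1 would also sweep in permitted prednisone, so the wording must exempt it.

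**The rule is strict.** Brief use at Week 1 would void a clearance at Week 11. This is true. Censoring at first use is a defensible alternative, and the all-counted sensitivity result shows how much the choice matters.

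**The study is exploratory.** It is descriptive with no hypothesis test, and 12 cases can be described individually. That removes any type I error concern but not the bias in an estimate meant for planning.

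**Conclusion.** The gap is real and should be closed; it does not invalidate the design. As written, a cessation first seen after a non-permitted BP-active treatment enters the primary estimate. Relative to carrying that patient as not ceased, this can only increase the number ceased and shorten, or leave unchanged, the Kaplan-Meier median. A mean over observed times alone has no such fixed direction.

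The size is unknown because the documents give no rate of prohibited use. On the assumed data, one affected patient moves the median from 6 to 8 weeks and three leave it unreached. Another set of counts, with five other cessations and two after prohibited use, gives 7/12 (58%) with the median reached if all are counted, and 5/12 (42%) with the median not reached if the two are not. That example was chosen to straddle the six events needed to reach a median, so it shows what is possible, not what to expect. A reader might infer that the trial's result will be materially biased; the documents do not support going that far.

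**What to change.** In the Statistical Analysis Plan:

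1. State that a cessation first seen after on-study use, for any indication, of a non-permitted BP-active treatment in Table-1 is not an event in the primary summary, and that the patient is carried as not ceased to Week 12. Name the treatments: topical corticosteroid, topical calcineurin inhibitor, tetracycline, niacinamide, methotrexate, azathioprine, mycophenolate, cyclosporine, and corticosteroid outside the permitted baseline and rescue prednisone. A cessation seen before that use still counts.
2. Report the analysis that counts all cessations as a sensitivity result.
3. Use a time summary that can hold patients who have not ceased, such as a Kaplan-Meier median with its confidence interval, in place of means and standard deviations.
4. Show the Week 12 BPDAI change with and without values recorded after such use.
5. List drug, indication and start and stop dates for each case.
6. State separately how permitted prednisone is handled.

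Footnote † and all clinical management are unchanged.

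**Cost.** SAP text, one listing and one sensitivity result. Data collection may also need an addition: Table-2 has no concomitant-medication row, and Concomitant Medications explicitly requires recording only of bland emollients. The estimate may be less favourable, and the rule is strict for brief early use. Settling it before the data are seen avoids a choice made afterwards in an open-label study.
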